PepCan was first tested in human to treat biopsy-proven high-grade squamous intraepithelial lesions (HSILs) in a Phase I single-arm, single-site study (NCT01653249). Subjects (n=52) were enrolled between September 2012 and January 2015, and those with biopsy-proven cervical intraepithelial neoplasia (CIN) 2/3 (n=34) (synonymous to HSIL) were eligible for vaccination. The initial part of the clinical trial was doseescalation in style in which six subjects each were consecutively assigned to increasing amounts of HPV-16 E6 peptides (50 μg/peptide, 100 μg/peptide, 250 μg/peptide, and 500 μg/peptide). The amount of Candin® was constant at 300 µL. After the dose escalation phase, an additional 10 subjects were vaccinated at the optimal dose of 50 µg/peptide as determined by histological regression. At the screening visit, the cervix was visualized under a colposcope after applying acetic acid, biopsies were obtained, Thin-Prep (Hologic, Marlborough, MA) was collected for HPV-DNA testing (Linear Array HPV Genotyping Test, Roche Molecular Diagnostics, Pleasanton, CA), and routine laboratory testing was performed (complete blood count, sodium, potassium, chloride, carbon dioxide, blood urea nitrogen, creatinine, aspartate transaminase, alanine transaminase, lactate dehydrogenase, γ-glutamyl transpeptidase, total bilirubin, and direct bilirubin). Subjects who already were diagnosed with biopsy-proven CIN2/3 were also eligible as long as the first vaccine injection could be given within 60 days, and other inclusion criteria were met (ages 18 to 50 years old, blood pressure ≤ 200/120 mm Hg, heart rate 50 to 120 beats per minute, respiration \leq 25 breaths per minute, temperature \leq 100.4°F, white count \geq 3 x 109/L, hemoglobin \geq 8 g/dL, and platelet count ≥ 50 x 109/L). Being positive for HPV-16 was not required due to possible crossprotection [19, 20, 22, 23] and de novo immune stimulation [24, 25]. Exclusion criteria included a history of disease or treatment causing immunosuppression, pregnancy, breast-feeding, allergy to Candida, a history of severe asthma, current use of beta-blocker, and a history of invasive squamous cell carcinoma of the cervix. Urine pregnancy test was performed prior to each injection, and blood was drawn for routine laboratory testing and immunological assessments immediately prior to the first and third injections. The vaccine was administered intradermally in any limb. Twelve weeks after the last injection, blood was drawn, ThinPrep sample was collected and LEEP was performed. The study gynecologists described the presence of visible lesions and their locations. Digital photographs were taken as additional documentation. Pre-vaccination biopsies from the screening visits and post-vaccination LEEP biopsies were read by the staff pathologists at the study institution. In addition, the study pathologist reviewed all slides of all LEEP samples. The highest grade of pathology found in any lesion was used to determine eligibility to be vaccinated and to assess histological response. Safety and tolerability were assessed from the time informed consent was obtained until the day LEEP was performed using the National Cancer Institute Common Terminology Criteria for Adverse Events (NCI CTCAE) Version 4.0. Dose-limiting toxicities were defined as vaccine-related allergic and autoimmune AEs greater than grade 1 and any other AEs greater than grade 2. Efficacy was based on histological grading of the LEEP samples. A subject with no dysplasia or cervical intraepithelial neoplasia 1 (CIN 1) was considered to be a complete responder, and a subject with CIN2/3 measuring ≤ 0.2 mm2 was considered to be a partial responder (ScanScope® CS and ImageScope™ software, Aperio, Vista, CA). When responders and non-responders were compared, complete and partial responders were combined.

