Figure 2: FACS analysis of peripheral immune cells. Upper panel: Systemic Th1, Th2, and Treg before, after 2, and after 4 vaccinations. Lower panel: Responders are indicated by filled circles and non-responders by filled squares. None of the subjects with pre-vaccination Treg levels ≥0.7% was a vaccine responder. Cells were first stained with antibodies for surface markers CD3, CD4, and CD25. Staining for intracellular T-bet, GATA3, and Foxp3 was performed with the Foxp3 staining kit according to the manufacturer's instructions (eBioscience). Th1 cells were expressed as a percentage of CD4 cells positive for T-bet, Th2 cells as a percentage of CD4 cells positive for GATA3, and Tregs as a percentage of CD4 cells positive for CD25 and Foxp3. Paired t-test (upper panel) or Wilcoxon rank-sum test (lower panel) was used.

A follow-up clinical trial, "A Phase II Clinical Trial of PepCan Randomized and Double-Blinded to Two Therapy Arms for Treating Cervical High-Grade Squamous Intraepithelial Lesions", is ongoing in which eligible subjects are treated with PepCan or Candin® to prevent progression to cervical cancer (NCT02481414). Instead of performing LEEP at 3 months, the subjects are being observed for 12 months. Four quadrant cervical biopsies are being performed to assess histological responses. No serious toxicity has been reported to date.

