3. OBJECTIVES AND ENDPOINTS

OBJECTIVES	ENDPOINTS	JUSTIFICATION FOR ENDPOINTS
PRIMARY		
Determine the safety of a	Careful monitoring of adverse events	Investigators will use NCI CTCAE
7-injection scheduling of	(AEs) at all ten (10) visits (2 years)	Version 5.0 to assess AEs and
PepCan regimen.	based on NCI CTCAE Version 5.0.	evaluate the safety of PepCan.
SECONDARY		
Determine the efficacy of	The absence of recurrence will be	The goal of PepCan vaccine is to
a 7-injection PepCan	assessed at all ten (10) visits (2 years).	reduce recurrence of head and
regimen.	Recurrence rates will be compared	neck cancer.
	between the PepCan and placebo arms.	
TERTIARY		
Determine immunological	T-cell (ELISPOT assay) and immune	Immunological responses are
responses to a 7-injection	regulatory cell responses (FACS	important in preventing cancer
PepCan regimen.	analysis) at Visits 1, 5, 8, and 9 will be	recurrence.
	assessed before and after vaccination.	
EXPLORATORY		
Compare the profile of	DNA sequencing methods will be	Diversity of gut microbiome is
gut and oral microbiome	utilized. Stool samples will be analyzed	now recognized to be associated
before and after PepCan	after Screening Visit, and Visits 5, 7, and	with favorable response to
regimen.	8. Oral wash samples will be analyzed at	cancer immunotherapy [27].
	Screening Visit, and Visits 5, 7, and 8.	

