8.2 STATISTICAL ANALYSES

Subjects who received at least one dose of the vaccine will be included in safety assessments. Safety analyses will include summaries of the incidence of AEs using the NCI CTCAE Version 5.0 that occur during the study period regardless of causality. The AEs will be mostly descriptive initially. However, after unblinding at the completion of the study, rates of common side effects (occurring with 5% or more injections) will be compared between the PepCan and the placebo arms. Efficacy will be assessed by comparing cancer recurrence rate between the 2 arms. The expected number of head and neck cancer patients who achieve remission is 100 patients per year. For immunological assessments, the presence of new anti-HPV-16 E6 T-cell activity will be measured using CD3 ELISPOT assay, and its statistical significance will be assessed using a paired *t*-test. For analyses of immune cells such as Th1, Th2, Treg, and MDSCs, percentages before and after vaccination will also be assed using a two-tailed paired *t*-test. The frequencies between subjects who experience recurrence and those that do not in the PepCan arm will be compared using Wilcoxon rank-sum test. The diversity of gut microbiome will be assessed prior to

injection, and will be compared to that after injection using alpha diversity, beta diversity, and compositions at the phylum or family levels. These parameters will also be compared between subjects with and without recurrence with in the PepCan arm.

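### Section 8.2 plans no PepCan versus placebo comparison of immune-cell percentages or gut microbiome, so recovery after cancer therapy cannot be separated from a vaccine effect.

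*Combined protocol and SAP*

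**What the plan says.** The trial is randomised 3:1, double-blind and placebo-controlled (section 4.1). Section 8.2 sets out these analyses of the immune and microbiome endpoints:

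- **Immune cells (Th1, Th2, Treg, MDSC), before/after:** "percentages before and after vaccination will also be assed using a two-tailed paired" t-test.
- **Immune cells, by outcome:** "The frequencies between subjects who experience recurrence and those that do not in the PepCan arm will be compared using Wilcoxon rank-sum test".
- **Gut microbiome, before/after:** the pre-injection state "will be compared to that after injection using alpha diversity, beta diversity, and compositions at the phylum or family levels".
- **Gut microbiome, by outcome:** "These parameters will also be compared between subjects with and without recurrence with in the PepCan arm".

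A PepCan versus placebo comparison is named for two things only. One is recurrence (sections 7.3 and 8.2). The other is safety, where "rates of common side effects (occurring with 5% or more injections) will be compared between the PepCan and the placebo arms". The objectives table in section 3 has the same before/after framing: the T-cell and immune regulatory cell responses are to be "assessed before and after vaccination". Section 8.2 limits the recurrence-status analyses to the PepCan arm but names no arm for the paired tests.

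Section 11.1 has one schedule for all subjects: immune blood at Visits 1, 5, 8 and 9, and stool kits at Screening and Visits 5, 7 and 8.

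**The concern.** The paired design matches the sponsor's first trial of PepCan, which was run "in a Phase I single-arm, single-site study" and whose immune-cell figure states "Paired t-test (upper panel) or Wilcoxon rank-sum test (lower panel) was used". That trial had no concurrent control. This one does, and the plan does not use it for these endpoints.

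The control matters because of when subjects enter. Section 5.1 requires surgery, radiation and/or chemotherapy to have been completed within the previous 120 days, with no stated minimum interval. Immune cells and gut flora may still be changing after such treatment. A paired test in vaccinated subjects measures the vaccine effect plus that change and cannot separate the two. If both arms are pooled, it does not isolate the vaccine at all.

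At stake is the reading of the tertiary (immune) and exploratory (microbiome) results. Section 2.3 gives prolonging the Th1 shift as the reason for seven doses, so a Th1 rise wrongly credited to PepCan would bear on the rationale of the regimen.

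**Working it through.** **The plan's own figure.** The only sizing in the documents is for recurrence (section 8.1): 80% on placebo and 0.80 × (1 − 0.45) = 44% on PepCan. With 24 versus 72 subjects and a two-sided 5% test of two proportions (normal approximation, no continuity correction), power is 0.901, which reproduces the stated 90%. Nothing is sized for the immune or microbiome endpoints.

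**Subjects still sampled.** Under section 5.5 a subject with recurrence completes participation, so assume sampling only while recurrence-free, a constant hazard and no other loss. The recurrence-free fraction is S(t) = (1 − R)^(t/24), with t in months from Visit 1. Visit 4 is at 9 weeks (2.07 months). Visit 5 is then at 5.07 months and Visit 8 at 2.07 + 3 + 3 + 3 + 6 = 17.07 months.

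| | S(t) | PepCan (of 75) | Placebo (of 25) |
|---|---|---|---|
| Visit 5, R = 80% | 0.712 | 53.4 | 17.8 |
| Visit 8, R = 80% | 0.318 | 23.9 | 8.0 |
| Visit 5, R = 44% | 0.885 | 66.4 | – |
| Visit 8, R = 44% | 0.662 | 49.7 | – |

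**Paired test with no vaccine effect.** Let d be a drift common to both arms, in SD of within-subject change. The documents give no value, so a range is shown. For n subjects the test rejects with probability P(|T| > t at 0.975 on n − 1 df), where T is noncentral t with noncentrality d√n. With no vaccine effect on recurrence either, R = 80% in both arms:

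| Drift d | Visit 5, PepCan n = 53 | Visit 8, PepCan n = 24 |
|---|---|---|
| 0 | 5% | 5% |
| 0.1 | 11% | 8% |
| 0.2 | 30% | 16% |
| 0.3 | 57% | 29% |
| 0.5 | 95% | 65% |

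The unstated arm changes these figures. With no loss at all, 72 PepCan subjects give 13%, 39%, 71% and 99% for d = 0.1, 0.2, 0.3 and 0.5. Pooling both arms (96) gives 16%, 49%, 83% and above 99%.

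**Between-arm test.** Write the expected change as (vaccine effect + d) on PepCan and d on placebo. The difference is the vaccine effect alone, so a shared drift cancels. The test holds near 5% if loss to recurrence is equal between arms or unrelated to immune change. Otherwise it does not hold exactly. A simulation (6,000 runs per setting, 75 versus 25 randomised, pre/post correlation 0.5, recurrence 44% versus 80%, recurrence liability correlated 0.3 to 0.7 with immune change) gave ANCOVA rejection rates of 6–9% at Visit 5 and 7–18% at Visit 8.

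**Precision of the between-arm test.** Here the sizing assumption of 44% versus 80% recurrence is used, which is a different scenario from the paired-test table. The unadjusted detectable difference at 80% power is about (1.960 + 0.842) × √(1/n₁ + 1/n₂):

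- Visit 5, 66 versus 18: 2.802 × 0.266 = 0.745 SD; 0.754 with the t distribution.
- Visit 8, 50 versus 8: 2.802 × 0.381 = 1.07 SD; 1.086 with the t distribution.

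**The case against.** **The plan never says that a paired change will be attributed to PepCan.** True. Section 3 defines these endpoints as before/after, and efficacy rests on the between-arm recurrence test. A reader might infer that the efficacy or safety conclusions are compromised. They are not: both have their own arm comparison. What remains is that an objective to determine the immune response to the regimen cannot be met by a change with no control.

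**Before/after is not the only analysis.** Also true. The comparisons by recurrence status exist, but they stay inside the PepCan arm and so do not supply a control.

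**If the paired tests were run in each arm, placebo drift would be visible.** Possibly. The text does not say so, and two separate paired tests with very different numbers do not make a comparison.

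**Drift may be small.** Visit 1 can be up to 90 days after screening, so the immune baseline may be as late as about 120 + 90 = 210 days after therapy. That is a maximum, and the stool baseline is tied to screening. Antibiotic questionnaires are collected to help interpret the microbiome (section 7.6), but section 8.2 has no step that uses them. The size of any drift is unknown, which is why only a range is given.

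**The endpoints are low in the hierarchy and partly optional.** Section 7.3 words the FACS and microbiome diversity work permissively. This lowers the weight, although section 3 lists both as endpoints.

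**ELISPOT has internal controls.** Positivity is judged against negative-control wells, and the t-test is by region, only where the positivity index rises. It may be a within-subject responder call. A reader might extend the percentages above to ELISPOT; the documents do not support that.

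**A between-arm test is imprecise and, late on, compares survivors.** This stands, and it shapes the fix.

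**Conclusion.** The gap is real and cheap to close. Section 8.2 plans no PepCan versus placebo comparison of immune-cell percentages or gut microbiome and does not say which arm the paired tests use. Followed as written, it leaves change after cancer therapy inseparable from a vaccine effect in the tertiary and exploratory results, while suitable control samples go unused for that purpose.

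The false-positive rates illustrate the mechanism and do not forecast it. They rest on an assumed drift, a PepCan-only test, constant-hazard recurrence of 80% in both arms and no other loss. A reader might take the larger Visit 5 figures as the trial's actual error rate. The documents contain no drift or SD that would support this, and the rates are lower at Visit 8, the first immune sample after all seven injections.

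**What to change.** In section 8.2:

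1. State that change from baseline in immune-cell percentages and gut alpha diversity will be compared between PepCan and placebo, adjusted for the baseline value (Visit 1 for blood, Screening for stool). ANCOVA at Visit 5, the best-populated time point, would serve. Give Visit 8 as an estimate with a 95% CI and a caution that recurrence may deplete the arms unequally.
2. For ELISPOT, compare between arms the proportion of subjects with at least one new positive E6 region, a summary already used in the Phase I trial.
3. Keep the paired tests as within-arm description, name the arm they apply to, and label all these analyses supportive.

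The wording should be settled before unblinding.

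The cost is SAP text and a little more analysis, with no new samples or visits. The price is precision: 80% power needs about 0.75 SD unadjusted at Visit 5 (66 versus 18) and about 1.1 SD at Visit 8 (50 versus 8). Visit 8 should therefore be read as an estimate and not as a well-powered test.

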Therefore, in this Phase I/II clinical trial of PepCan in subjects with head and neck cancer who achieved remission, the subjects in the vaccination arm will be given 7 doses of PepCan, so the duration of Th1 shift will be prolonged. The main goal would be to assess the safety and efficacy of giving 7 total doses of PepCan. For the assessment of efficacy, a randomized double-blind placebo-controlled design will be used in which the subjects will receive PepCan versus placebo at a 3:1 ratio. The first 4 doses will be given every 3 weeks, and the remaining 3 doses will be given every 3 months.

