5.5 RECURRENCE

If a subject has clinical and/or radiological evidence of recurrence and a study physician determines the subject to be in recurrence, the subject will not receive further study interventions. The subject will be included in the recurrence group, and will complete participation by filling out the "Recurrence Questionnaire".

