Subjects may choose to allow future use of remaining samples in the informed consent form. After all tests are completed, any leftover samples will be saved for future research studies on HPV. The blood, cell, oral, and stool samples will be frozen and will be stored with only the subject identifier. The cell samples may be stored indefinitely until needed for a future research study. Subjects who originally chose to allow future use of remaining samples but change their mind later may notify the PI in writing to the address listed in the informed consent form. The subject identifier will be linked to the subject's name and the study team will collect the sample and destroy it per institutional guidelines.

LABORATORY EVALUATIONS

BLOOD SAMPLES

Complete blood count with differential, Chem 7, and liver function tests will be performed at [INSERT LOCAL LAB] in accordance with their current SOPs.

FACS ANALYSIS

Peripheral blood mononuclear cells (PBMCs) isolated from blood samples drawn at Visits 1, 5, 8, and 9 may be analyzed at UAMS to measure circulating immune cells such as Th1, Th2, regulatory T-cell (Treg), and myeloid-derived suppressor cells (MDSCs). HLA typing may be performed using remaining PBMCs.

ELISPOT

An immune assay such as an ELISPOT assay to assess the presence of HPV-specific T-cells will be performed. After each blood draw, PBMCs will be separated into CD14+ and CD14- populations and cryopreserved. To eliminate inter-assay variability, all 4 blood samples (before vaccination, after 4 vaccinations, 7 vaccinations, and at the end of the study) will be used to establish T-cell lines and to

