8. STATISTICAL CONSIDERATIONS

8.1 DETERMINATION OF SAMPLE SIZE

The recurrence rate of head and neck cancer is 80% over 2 years (50 to 60% local recurrence and 20 to 30% distant recurrence [41]. In the Phase I trial of PepCan described above the overall histological regression rate of HSILs was 45% [36]. A reduced recurrence rate by the magnitude of 45% would reach 44%. Vaccinating 72 subjects in the PepCan arm and 24 subjects in the placebo arm would have 90% power at alpha of 5%, 2 tailed. Accounting for about 5% drop out rate, 75 subjects would be needed in the PepCan arm, and 25 subjects in the placebo arm.

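### The late immune samples (Visits 8 and 9) come only from subjects still free of recurrence, and the planned paired t-tests do not allow for that selection; the bias could go either way.

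*Combined protocol and SAP*

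**What the plan says.** - **Sampling.** Research blood for ELISPOT and FACS is drawn at Visits 1, 5, 8 and 9 (sections 3 and 7.3). The last injection is at Visit 7, so Visits 8 and 9 are the only research samples after all seven doses.
- **Recurrence.** Under section 5.5 a subject judged to be in recurrence gets no further study intervention and "will complete participation by filling out the" Recurrence Questionnaire. Subjects stopped for toxicity, by contrast, stay on the assessment calendar, labs included (sections 7.2 and 9.2).
- **Tests.** For Th1, Th2, Treg and MDSC, section 8.2 says that "percentages before and after vaccination will also be assed using a two-tailed paired" t-test; it names neither visit nor arm. Section 7.3 plans paired t-tests for ELISPOT comparing baseline with the samples after four doses, after seven doses and at the end of the study.
- **Not stated.** Section 8.2 has no rule for samples missing because of recurrence and no PepCan-placebo comparison of immune change.
- **Purpose of the late samples.** Section 2.3 says that how long the Th1 shift lasts is unknown, and gives seven doses "so the duration of Th1 shift will be prolonged".

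**The concern.** A paired t-test at Visit 8 or 9 uses only subjects who have both a baseline and a late sample, which in practice means those not yet in recurrence. Section 3 justifies the immune endpoint on the ground that immune responses help to prevent recurrence. If so, the subjects who remain may be selected on the quantity being tested, and their mean change need not be the mean change in everyone vaccinated. The question at stake is the one behind the seven-dose regimen: whether the immune shift lasts. A late rise, or its absence, could reflect who is left as well as what the vaccine did.

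**Working it through.** **1. The plan's rates.** Section 8.1 states "The recurrence rate of head and neck cancer is 80% over 2 years" for controls and a 45% relative reduction, so the PepCan rate is 0.80 × (1 − 0.45) = 0.44. The stated power (90%, 72 v 24, "alpha of 5%, 2 tailed") reproduces:
- Pooled rate = (72 × 0.44 + 24 × 0.80) / 96 = 0.53
- Null SE = √[0.53 × 0.47 × (1/72 + 1/24)] = 0.1176
- Alternative SE = √(0.44 × 0.56/72 + 0.80 × 0.20/24) = 0.1004
- z = (0.36 − 1.96 × 0.1176) / 0.1004 = 1.29, which is 90.1% power

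That power concerns recurrence. No power or sample size is given for the immune analyses.

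**2. Who is left at two years** (no other dropout):
- PepCan, vaccine works as assumed: 75 × (1 − 0.44) = 42
- PepCan, vaccine does nothing: 75 × (1 − 0.80) = 15
- Placebo: 25 × (1 − 0.80) = 5

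By visit, assuming a constant hazard, the recurrence-free share is (1 − r)^(t/24), with Visits 5, 8 and 9 at about 5.1, 17 and 23 months:

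| Group | Visit 5 | Visit 8 | Visit 9 |
|---|---|---|---|
| PepCan of 75, r = 44% | 66 | 50 | 43 |
| PepCan of 75, r = 80% | 53 | 24 | 16 |
| Placebo of 25, r = 80% | 18 | 8 | 5 |

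A subject whose recurrence is found at Visit 8 or 9 itself may still give that sample, so these counts are approximate.

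**3. False positives if recurrence depends on the change.** The documents give no figure for this link, so it is an assumption shown over a range. Simulation: 75 subjects, change ~ N(0,1) with true mean zero, probability of recurrence logistic in the change, and a two-sided 5% one-sample t-test on the change in those without recurrence.

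| Odds ratio per SD of change | 44% recurrence | 80% recurrence |
|---|---|---|
| 1.5 | about 20% | 20% to 22% |
| 2 | 44% to 46% | 48% |

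At an odds ratio of 1 the 44% case returns about 5%, as it should. At an odds ratio of 2 the survivors' mean change is +0.28 SD (44% recurrence) or +0.52 SD (80%). If half the variance is assay noise, the 44% column falls to about 12% and 24%.

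A milder model, with individual slopes and a hazard ratio of 0.67 to 0.50 per SD of the current marker level, gives false rises in 7% to 12% of trials (44% recurrence) or 11% to 19% (80%), against a nominal 2.5%.

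**4. Other forms of the link.**
- Recurrence depends on a stable level, or on the current level of a stationary marker: mean shift zero, false-rise rate 2% to 3%.
- Recurrence depends on the baseline value only, high being protective, hazard ratio 0.67 to 0.50 per SD: the shift is downward, −0.11 to −0.18 SD at 44% recurrence and −0.28 to −0.42 SD at 80%.

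**5. A between-arm contrast at Visit 9.** With 80% recurrence in both arms and no marker effect, its false-positive rate is 4% to 5%, because the selection is the same in both arms. If recurrence is 44% v 80%, the selection differs: at an odds ratio of 2 the contrast is shifted by 0.28 − 0.52 = −0.24 SD, against PepCan.

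**6. A likelihood model that also uses Visit 5.** The false-positive rate is about 5% if loss depends on the Visit 5 change. It is about 25% to 28% at an odds ratio of 2 if loss depends on the unseen Visit 9 value (18% to 32% in separate runs with visit correlations of 0.5 to 0.7).

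**The case against.** The strongest reply is that a paired test already cancels stable differences between subjects who recur and those who do not. Bias needs a link between recurrence and the within-subject change, and the documents give no size for one. This stands. A reader might infer that late results must be biased upward, but section 3 says only that immune responses matter for preventing recurrence, and the phase I marker evidence in section 2.1 includes a pre-vaccination Treg difference between responders and non-responders. A baseline link of that kind could leave no bias or reverse it, depending on the marker.

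Three other strong readings are not supported:
- **That a PepCan-placebo contrast cannot remove the selection.** If the vaccine does nothing, both arms lose 80% and the contrast holds its level. It fails only if the arms differ in recurrence.
- **That ELISPOT is limited to complete sets of four.** Section 7.3's wording, "all 4 blood samples (before vaccination, after 4 vaccinations, 7 vaccinations, and at the end of the study) will be used", is tied to inter-assay variability. It describes running a subject's samples together and does not exclude incomplete sets. The ELISPOT t-test follows the text on triplicate wells and can also be read as a within-subject test by region, which survivor selection would not distort. The section 8.2 test of cell percentages is not open to that reading.
- **That Visit 5 should become the main immune time point.** It has the least loss, but its blood is drawn at the visit of the fifth injection and so reflects four doses, whereas the tertiary objective concerns seven.

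It is also fair that this is a tertiary outcome, that FACS is described as something that may be done, and that no decision rule rests on it. That limits the weight of the point but does not remove it.

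**Conclusion.** The point holds in a limited form. By design, late immune pairs come only from recurrence-free subjects. On the plan's own rates that is about 42 or 15 of 75 PepCan subjects at Visit 9, depending on whether the vaccine works, and about 5 of 25 on placebo. The planned paired t-tests take no account of this. Whether bias follows, and in which direction, depends on an unquantified link between immune change and recurrence. For assumed odds ratios of 1.5 to 2 per SD of change, with no true change, the false-positive rate is about 20% to 48% in place of 5%; under other plausible links it is nominal, or the bias is downward. The counts assume section 8.1's rates and no other dropout. This is worth correcting because the late samples carry the question of durability and the correction is cheap.

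**What to change.** In section 8.2:
1. Replace the separate completer paired t-tests with one mixed model for change from Visit 1 at Visits 5, 8 and 9, using every available sample and including arm.
2. Report a PepCan-placebo contrast from that model. State that it removes the selection if the arms have equal recurrence but not if the vaccine reduces recurrence, and that few placebo subjects remain at Visit 9.
3. Label raw Visit 8 and 9 results as being among recurrence-free subjects, give the number of subjects at each visit, and show the Visit 5 change separately for those who did and did not reach Visit 9.

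The cost is SAP wording and modest programming on samples already scheduled, with no new visits or subjects. The limit should be stated in the plan: the model corrects fully only if loss depends on observed values. If it depends on the unseen Visit 9 value, about 25% to 28% false positives remain at an odds ratio of 2.
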